OBJECTIVES	ENDPOINTS (OUTCOME MEASURES)			
29.				
 Non-invasive ventilation/high-flow oxygen: Non-invasive ventilation/high-flow oxygen use up to Day 29. Incidence and duration of new non-invasive ventilation or high-flow oxygen use through Day 29. 	• Days of non-invasive ventilation/high- flow oxygen (if applicable) up to Day 29.			
 Invasive Mechanical Ventilation/ ECMO: Ventilator/ECMO use up to Day 29. Incidence and duration of new mechanical ventilation or ECMO use through Day 29. 	 Days of invasive mechanical ventilation/ECMO (if applicable) up to Day 29. 			
 Proportion of subjects alive and without respiratory failure at Day 29. 	 Proportion of subjects who did not meet either of the following two categories on Day 29: 7. Hospitalized, on invasive mechanical ventilation or ECMO; 8. Death. 			
 Hospitalization: Duration of hospitalization (days). 	• Days of hospitalization up to Day 29.			
 Mortality: 14-day mortality. 29-day mortality. Time to death up to Day 29. 60-day mortality. 	• Date and cause of death (if applicable).			
• Markers of inflammation and coagulation.	 C-reactive protein (CRP), ferritin, D- dimer, and fibrinogen on Day 1; Days 3, 5, 8, and 11 (while hospitalized); and Days 15 and 29 (if attends in-person visit or still hospitalized). 			
 2. To evaluate the safety of risankizumab as compared to the control arm as assessed by: Cumulative incidence of SAEs through Day 60. Cumulative incidence of Grade 3 and 4 clinical and/or laboratory AEs through Day 60. 	SAEs.Grade 3 and 4 AEs.			

OBJECTIVES	ENDPOINTS (OUTCOME MEASURES)		
 Discontinuation or temporary suspension of study product administration (for any reason). Changes in white blood cell (WBC) count with differential, hemoglobin, platelets, creatinine, total bilirubin, alanine aminotransferase (ALT), aspartate aminotransferase (AST), and international normalized ratio (INR) over time (analysis of lab values in addition to AEs noted above). 	 Episodes of early discontinuation or interruption of study product administration. WBC with differential, hemoglobin, platelets, creatinine, total bilirubin, ALT, AST, and INR on Day 1; Days 3, 5, 8, and 11 (while hospitalized); and Days 15 and 29 (if attends in-person visit or still hospitalized). 		
Exploratory			

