8.1.2.1 Measures of Clinical Support, Limitations, and Infection Control

The subject's clinical status will be captured on each study day while hospitalized up until and including Day 29. Once subjects are discharged from the hospital, they will have a study visit on Days 8, 15, 22, 29, and 60 visits (only the ordinal score will be obtained on Day 60) as an outpatient. The Day 8, Day 22 and Day 60 visits do not have laboratory tests or collection of samples and may be conducted by phone. Day 15 and 29 visits are preferred to be in person in order to collect safety laboratory testing, stored samples, and virologic assessments but may be performed. Clinical status is largely measured by the ordinal scale. The ordinal scale can also be evaluated over the phone if the discharged subject is unable to return for in-person visits on Day 15 and 29.

The following measures are recorded for the ordinal scale. See MOP for more detailed description of ventilatory devices in each category:

- Hospitalization.
- Oxygen requirement.
- Non-invasive mechanical ventilation (via mask) requirement.
- High-flow oxygen requirement.
- Invasive mechanical ventilation (via endotracheal tube or tracheostomy tube) requirement.
- ECMO requirement.
- Ongoing medical care preventing hospital discharge (COVID-19 related or other medical conditions).
- Limitations of physical activity (self-assessed and reported as new or increased limitations as compared to status prior to the onset of COVID-19).
- Isolated for infection control purposes.

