- Clinical status assessed using ordinal scale on Study Days 1, 3, 5, 8, 11, 15, 22, and 29;
- Change in clinical status using change in ordinal scale from Study Day 1 to Study Days 3, 5, 8, 11, 15, 22, and 29;
- Days of supplemental oxygen or worse (i.e., ordinal score of 5, 6, 7, 8) up to and including Study Day 29;
- Days of non-invasive ventilation/high-flow oxygen or worse (i.e., ordinal score of 6, 7, 8) up to and including Study Day 29;
- Whether a subject who has a baseline ordinal score of 5 requires new non-invasive oxygen use or worse (i.e., ordinal score of 6, 7, 8) during the study up to and including Study Day 29 (incidence);
- Days a subject who has a baseline ordinal score of 5 has an ordinal score of 6 or greater up to and including Study Day 29;
- Days of invasive mechanical ventilation/ECMO or worse (i.e., an ordinal score of 7 or 8) up to and including Study Day 29;
- Whether subject who has a baseline ordinal score of 5 or 6 requires new invasive ECMO use or worse (i.e., ordinal score of 7 or 8) during study up to and including Study Day 29 (incidence);
- Days a subject who has a baseline ordinal score of 5 or 6 has an ordinal score > 6 up to and including Study Day 29;
- Whether a subject is alive and without respiratory failure (ordinal score < 7) at Study Day 29;
- Time (days) to ventilation or death from Study Day 1 up to and including first 29 days of being on study.
- Days of hospitalization from date of admission up to and including Study Day 29.
- Values of C-reactive protein (CRP), ferritin, D-dimer, lactate dehydrogenase (LDH), and fibrinogen on Study Days 1, 3, 5, 8, and 11 (while hospitalized); and Study Days 15 and 29 (if attends in-person visit or still hospitalized).

Safety

- Whether a subject died from Day 1 up to and including Study Day 15.
- Whether a subject died from Day 1 up to and including Study Day 29.
- Whether a subject died from Day 1 up to and including Study Day 60.
- Time (days) to death from Study Day 1 up to and including Study Day 29.

- Whether a subject experienced at least one SAE up to and including Study Day 60.
- Whether a subject experienced at least one Grade 3 or Grade 4 AE up to and including Study Day 60.
- Episodes of early discontinuation or interruption of study product administration.

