11. Proportion of subjects alive and without respiratory failure at Study Day 29;	Primary	
 Use the complete data for ordinal score to define survival without respiratory failure. Subjects will be considered events at Day 29 if they are dead or are on invasive mechanical ventilation/ECMO anytime between Day 26 and Day 32 (Window for Day 29) regardless of their baseline ordinal score. All subjects who died before Day 26 (beginning of Day 29 visit window) will be considered events. All subjects who died after Day 32 or those who were not on invasive mechanical ventilation/ECMO between Day 26 and Day 32 will be considered non-events.
12. Time (days) to ventilation or death up to and including Day 29;	Primary	
 Use the complete data for ordinal score to define survival without respiratory failure. All subjects whose last assessment in the study is before Day 26 and before progression to mechanical ventilation or death will be considered non-events and censored at the date of their last observed assessment. Subjects who complete follow-up without mechanical ventilation or death will be censored at the expected study Day 29. Subjects whose last assessment in the study is before Day 29 but within window for Day 29 (i.e., Day 26, 27, 28) and before experiencing death or progression to mechanical ventilation will be considered non-events regardless of their discharge status at Day 29.
	Primary with Sensitivity Imputation	
 Use the complete data for ordinal score to define survival without respiratory failure. Subjects whose last assessment in the study is before Day 26 and were discharged to a location other than LTAC, hospice care or other hospital, or progressed to mechanical ventilation or death after Day 29 will be considered non-events and censored at Day 29. Subjects whose last assessment in the study is before Day 26 and before progression to mechanical ventilation or death and without being discharged to a location other than LTAC, hospice care or other hospital at their last assessment will be considered non-events and censored at the date of their last observed assessment. Subjects who complete follow-up without mechanical ventilation or death will be censored at the expected study Day 29.

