Ventilator / ECMO days will be defined as the number of days where the ordinal score > 6 up to and including Study Day 29. The total number of days will be the sum of all reported days, regardless of whether the days occur consecutively or in disjoint intervals. For planned gaps between study days, the day of the qualifying Study Day and the days to the next planned Study Day will be included in the total number of days. The Post-Discharge Supplemental Oxygen CRF questions regarding days of ECMO or invasive ventilation will be used for any time period the subject is not hospitalized at the study hospital. See Section 6.5 for the plan for handling subjects who do not have data through Study Day 29 or die prior to Study Day 29.

Duration of Invasive Mechanical Ventilation/ECMO days will be summarized in a table using medians and quartiles by treatment (Table 38). Bee swarm plots of Invasive Mechanical Ventilation/ECMO days, and days hospitalized by treatment will be generated (Figure 21).

The incidence of new Invasive Mechanical Ventilation/ECMO use will be analyzed by treatment (Table 41). The numerator will only include subjects in category 6 or below at enrollment who change to a category 7 or 8. The denominator will include subjects with a baseline ordinal score of 6 or below. The number of subjects reporting new use of Invasive Mechanical Ventilation/ECMO and the incidence rate along with 95% and 80% CIs estimated using the Blaker method will be reported.

Refer to Table 6 for a list of covariates and subgroup analyses for this endpoint. Refer to Table 7 for imputation methods to be applied to this endpoint.

Proportion of Subjects Alive and Without Respiratory Failure at Study Day 29

The proportion of subjects alive and without respiratory failure at Study Day 29 will be defined as the proportion of subjects with an ordinal score < 7 at any time between Day 26 through Day 32 (Visit window for Study Day 29 Visit). The proportion of subjects with respiratory Failure or death at Day 29 will also be provided. These proportions will be presented by treatment along with 95% and 80% Blaker CIs. Treatment differences will be evaluated using a logistic regression and the p-value will be presented (Table 31).

Refer to Table 6 for a list of covariates and subgroup analyses for this endpoint. Refer to Table 7 for imputation methods to be applied to this endpoint.

Time to Mechanical Ventilation or Death up to and Including Day 29

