15.3. Changes from Version 2.0 to Version 3.0 of the Master SAP

- All analyses of time to events (e.g., time to sustained recovery, time to death, time to mechanical ventilation or death) endpoints were updated to censor subjects without events at last assessment.
- A sensitivity analysis was added for time to recovery endpoint that considers subjects whose last assessment in the study is prior to Day 60 after discharge from the hospital to a location other than LTAC, hospice care or other hospital as recovered by Day 60. Their time to recovery will be the day the time of their first observed/imputed recovery score (i.e., 1, 2, 3) or the day of discharge, whichever comes first.
- A sensitivity analysis was added for survival without respiratory failure and time to mechanical ventilation or death that considers subjects lost to follow-up before Day 26 (beginning of Day 29 window) before event who were discharged to a location other than LTAC, hospice care, or other hospital as non-events and censors them at Day 29.
- The analyses for mortality were updated to use Kaplan Meier estimates instead of crude estimates for mortality rates. All subjects lost to follow up before death were censored at their last assessment.
- A sensitivity analysis was added for the 14-day mortality and time to death through Day 15 endpoints that consider subjects lost to follow-up before Day 13 (beginning of Day 15 window) before event who were discharged to a location other than LTAC, hospice care, or other hospital as non-events and censors them at Day 15. Similar sensitivity analyses were added for 28-day mortality, 59-day mortality, time to death by Day 29, and time to death by Day 60 endpoints.
- The definition for survival without respiratory failure at Day 29 was updated count respiratory failure events and deaths that occurred within the Day 29 visit window (Day 26 through Day 32) and to count all deaths that occurred before Day 29.
- The method for handling ties in time to event analyses was updated from Breslow to the Efron method for analyses based on Cox regression model.
- Tables for laboratory parameters without grading ranges (Eosinophils, monocytes, basophils) were removed.

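### Alive without respiratory failure at Day 29: SAP 8.2.2 and Table 7 classify in opposite ways any subject whose status changes within Days 26-32

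*SAP*

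**What the plan says.** The protocol's objectives table (section 3) gives the endpoint as a status on one day: "Proportion of subjects who did not meet either of the following two categories on Day 29", the two categories being invasive ventilation/ECMO and death. SAP section 3.2 has the same idea: "Whether a subject is alive and without respiratory failure (ordinal score < 7) at Study Day 29".

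The SAP then makes the endpoint operational in two places, both using the Day 29 visit window.

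- Section 8.2.2 states that the proportion "will be defined as the proportion of subjects with an ordinal score < 7 at any time between Day 26 through Day 32". It adds: "The proportion of subjects with respiratory Failure or death at Day 29 will also be provided". Results go to Table 31, with Blaker intervals and a logistic-regression p-value.
- Table 7, row 11 (section 6.5.1), makes subjects events "if they are dead or are on invasive mechanical ventilation/ECMO anytime between Day 26 and Day 32", and also counts every death before Day 26 as an event. Its last bullet says that deaths after Day 32 or "those who were not on invasive mechanical ventilation/ECMO between Day 26 and Day 32 will be considered non-events".

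Section 8.2.2 refers to Table 7 for imputation methods only. Neither place says which prevails if they differ.

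**The concern.** One score below 7 on any day of the window is enough for success under 8.2.2. One day of ventilation, or death, in the same window is enough for an event under Table 7. A subject can satisfy both.

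The consequence is more than untidy text. Section 8.2.2 is worded as the definition of the endpoint, and a programmer who follows it would report some subjects who die in the window as alive without respiratory failure. The proportions and the p-value in Table 31 would then depend on which section was programmed. If that choice were made after unblinding, it would be a post hoc choice.

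**Working it through.** The plan gives no power, sample size or event rate for this endpoint, so there is no figure to reproduce. The check is a logical one: can a subject meet both rules, and when?

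**Inputs**

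- Success: any score below 7 on Days 26-32 (SAP 8.2.2).
- Event: death, or a score of 7, on any of Days 26-32 (SAP Table 7, row 11).
- Scores available: in hospital, "clinical status will be captured on each study day while hospitalized up until and including Day 29" (Protocol 8.1.2.1), so up to four inpatient scores on Days 26-29. SAP Table 1 gives a discharged subject one scheduled Day 29 visit with a window of Days 26-32.
- Deaths: taken from the SAE form by date (SAP 4.5), so deaths on Days 30-32 are also known.

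**Typical cases**

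| Status in the window | 8.2.2 | Table 7 event rule |
|---|---|---|
| Score 5 throughout | success | non-event |
| Ventilated throughout | not a success | event |
| Died before Day 26 | not a success | event |
| Ventilated Day 26, off the ventilator by Day 28 | success | event |
| Score 5 on Day 26, ventilated Day 28 | success | event |
| Score 6 on Day 26, never ventilated, dead Day 30 | success | event |

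**All possible patterns**

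Let each day be A (alive, score below 7), V (score 7) or D (dead, permanent). With d days:

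- all paths: 2^(d+1) − 1
- success only (all A): 1
- event only (no A, that is, V on the first k days and then D, k = 0 to d): d + 1
- both: the remainder

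| | All paths | Success only | Event only | Both |
|---|---|---|---|---|
| d = 7 (Days 26-32) | 2^8 − 1 = 255 | 1 | 8 | 255 − 1 − 8 = 246 |
| d = 4 (Days 26-29) | 2^5 − 1 = 31 | 1 | 5 | 31 − 1 − 5 = 25 |
| d = 1 (one score) | 2^2 − 1 = 3 | 1 | 2 | 0 |

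Of the overlapping paths, d − 1 arise through death without ventilation: 6 for d = 7 and 3 for d = 4. The other 240 and 22 include ventilation. These are counts of logical patterns, not expected numbers of patients.

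**What follows**

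1. The rules agree for every subject with constant status or a single score. They disagree for every subject who has both a score below 7 and a ventilated or dead day in the window.
2. The disagreement runs one way. Every subject with no event in the window has a score below 7, so the 8.2.2 proportion can only equal or exceed the complement of the Table 7 events. The effect on the difference between arms can go either way.
3. If success means a score below 7 on all days of the window, the overlap is zero.

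**Table 7's own bullets**

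The last bullet rests on not being ventilated in the window and does not require survival. Taken literally, the Day 30 death in the last row of the first table is an event under the second bullet and a non-event under the last one. The same holds for deaths before Day 26, who are events under the third bullet. The bullet's other limb, death after Day 32, also catches a subject ventilated on Day 28 who dies on Day 40, whom the second bullet calls an event.

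**The case against.** The best case for the plan is that this is one loose phrase. Section 8.2.2 points to Table 7 for this endpoint, and Table 7 has separate event and non-event bullets. The SAP's summary of changes for version 3.0 (section 15.3) describes the intention to "count respiratory failure events and deaths that occurred within the Day 29 visit window (Day 26 through Day 32"), which agrees with Table 7. On this view 8.2.2 meant a score below 7 throughout the window. That is probably what was intended, and it shows which sentence to change. It does not remove the conflict: the text says any time, the cross-reference covers imputation only, and there is no precedence rule.

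The objection on reach also stands. Scheduled inpatient scores stop at Day 29, and a discharged subject normally has one visit in the window. For Days 30-32 the conflict arises mainly through dates of death.

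Three stronger readings are tempting, and the documents do not support them.

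- A reader might infer that the two rows of Table 31 will add to more than 100%. That requires each row to be programmed from a different rule. The logistic regression needs one binary outcome per subject, so the realistic risk is that the wrong rule is used for both rows.
- A reader might infer a number of misclassified subjects per arm by applying an assumed crossing rate to an assumed proportion ventilated or dead. The documents give neither figure. A base that includes deaths before Day 26 would also be wrong, because those subjects have no score below 7 in the window.
- A reader might infer from the protocol's Day 29 wording that inpatients should be classified on the Day 29 score alone. That would replace the window rule in both places. It is a different definition and is not needed to reconcile the two texts.

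**Conclusion.** The contradiction is real. For subjects whose status changes within Days 26-32, the two SAP rules give opposite answers, and 8.2.2 as written can count a death in the window as survival without respiratory failure. Table 7's non-event bullet has a related fault.

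The size cannot be estimated from the documents. With the planned 100 subjects per arm (SAP section 5), each affected subject changes that arm's proportion by 1/100, or one percentage point, always upward under 8.2.2.

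The consequence is limited to an other secondary endpoint analyzed without covariates (SAP Table 6). The Day 8 primary analysis is unaffected, as are the two key secondary endpoints and the decision to call the product promising. The global analysis in Table 9 is also unaffected, since it lists sustained survival without respiratory failure, the key secondary, and not this endpoint. The conclusion rests on reading both rules as written. The text should be corrected before unblinding.

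**What to change.** Make two text edits in the SAP.

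1. Section 8.2.2: define success as the exact complement of the Table 7 event rule, that is, alive through Day 32 and no score of 7 from Day 26 through Day 32. Respiratory failure or death in Table 31 is then everyone else in the analysis.
2. Table 7, row 11, last bullet: limit non-events to subjects who were both alive through Day 32 and not on invasive ventilation/ECMO on Days 26-32. State that a death after Day 32 is a non-event only if there was no ventilation in the window. Deaths by Day 32 without ventilation are then events only.

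The cost is a few lines of text. No new data, visits or subjects are needed, and no other analysis changes.

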5.1 Inclusion Criteria

- 1. Admitted to a hospital with symptoms suggestive of COVID-19 and requires ongoing medical care.
- 2. Subject (or legally authorized representative) provides informed consent prior to initiation of any study procedures.
- 3. Subject (or legally authorized representative) understands and agrees to comply with planned study procedures.
- 4. Male or non-pregnant female adult ≥ 18 years of age at time of enrollment.
- Illness of any duration and has laboratory-confirmed SARS-CoV-2 infection as determined by PCR or other commercial or public health assay (e.g., Nucleic Acid Amplification Test [NAAT], antigen test) in any respiratory specimen or saliva ≤14 days prior to randomization.
- 6. Illness of any duration, and requiring, just prior to randomization, supplemental oxygen (any flow), mechanical ventilation or ECMO (ordinal score 5, 6, or 7).
- 7. Women of childbearing potential must agree to either abstinence or use at least one acceptable method of contraception from the time of screening through 5 months post study IP dosing.

Note: Acceptable methods include barrier contraceptives (condoms or diaphragm) with spermicide, intrauterine devices (IUDs), hormonal contraceptives, oral contraceptive pills, and surgical sterilization.

8. Agrees not to participate in another blinded clinical trial (both pharmacologic and other types of interventions) for the treatment of COVID-19 through Day 29 (see Section 5.4 for more information about concurrent trial participation).

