1. PREFACE

A novel coronavirus designated severe acute respiratory syndrome coronavirus 2 (SARS-CoV-2) was first identified in December 2019 in Wuhan, China, and has since spread globally, resulting in an ongoing pandemic of Coronavirus Disease 2019 (COVID-19). Currently, remdesivir is the only FDA approved antiviral for the treatment of patients hospitalized with COVID-19, but even with this antiviral the mortality of COVID-19 remains high. Multiple putative therapeutics involving repurposed agents (licensed or in late development) have been proposed for treating COVID-19, but there is no way to evaluate many of these agents due to lack of suitable animal models that replicate human disease. There is an urgent need for rapid development and testing of interventions to treat COVID-19 in hospitalized patients. An adaptive platform trial is one approach to allow for accelerated testing and selection of promising therapeutic agents in order to meet ongoing public health needs. Each new intervention represents a new stage. Default elements are described in this Master Statistical Analysis Plan (SAP) and align closely with BET-A study. Any stage-specific elements will be detailed in the respective stage-specific appendix of the SAP, and these supersede the corresponding elements described in this Master SAP.

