6.4.2. Covariates for Secondary Endpoints

The main analysis for time to sustained recovery will use baseline steroid use and actual baseline ordinal score as covariates in a Cox regression model. P-value from the score test of this adjusted Cox model will be used to compare the covariate adjusted time to sustained recovery between treatment arms. This analysis will be referred to as the primary analysis of the time to sustained recovery endpoint. In the supplemental analysis, time to sustained recovery endpoint will be analyzed using baseline steroid use, actual baseline ordinal score, continuous age, and continuous duration of symptoms prior to enrollment as covariates in the Cox model.

Survival without respiratory failure up to and including Study Day 29 will be analyzed only for subjects with an actual baseline ordinal score of 5 or 6. The main analysis for this endpoint will use a logistic regression model adjusted for baseline ordinal score (5 vs 6/7), baseline dexamethasone use (yes or no), continuous

baseline CRP value, and continuous age as covariates. Additionally, the proportion of subjects who are alive and without respiratory failure up to and including Study Day 29 will be presented by treatment along with 95% and 80% CI estimated from Kaplan Meier. As a sensitivity analysis, survival without respiratory failure will be analyzed using a logistic regression model adjusting for baseline steroid use and actual baseline ordinal score as covariates. A supplemental analysis of this endpoint will use a logistic regression model adjusting for baseline steroid use, actual baseline ordinal, continuous age, and continuous duration of symptoms prior to enrollment.

The analysis of the time to mechanical ventilation or death will include baseline ordinal score (5 vs 6/7), baseline dexamethasone use (yes or no), baseline CRP value and age as covariates in the Cox regression model.

A detailed list of covariates and subgroup analyses to be performed for secondary endpoints is also provided in [Table 6](#).

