The time to mechanical ventilation or death up to and including Day 29 will be defined as the elapsed time (in days) from Study Day 1 to date of mechanical ventilation or death. Any subjects whose last assessment is prior to obtaining the event and prior to Day 26 (beginning of Day 29 window) will be censored at the date of their last observed assessment. For the sensitivity analysis of this endpoint, subjects whose last assessment is

prior to obtaining the event and who were discharged to a location other than LTAC, hospice care, or other hospital will be considered recovered and censored at Day 29. For both primary and sensitivity analysis of this endpoint, subjects who complete follow-up will be censored Day 29. Events that occur after Day 29 will be censored at Day 29. A table will present median time to event along with corresponding 95% and 80% confidence intervals for each treatment along with the hazard ratio estimate and score test p-value from a Cox-proportional hazard model (Table 42). The Cox model will include as covariates baseline ordinal score, baseline CRP value, continuous age, and baseline dexamethasone use. Differences in time-to-event endpoints by treatment will be summarized with Kaplan-Meier curves (Figure 11). Analyses will be performed on the mITT population for those subjects who at baseline have an ordinal score of 5 or 6, CRP<150 mg/L, and age<85 years and results will be reported in Table 42. This analysis will be repeated for all subjects in the mITT population and results will be reported in Table 43.

Refer to Table 6 for a list of covariates and subgroup analyses for this endpoint. Refer to Table 7 for imputation methods to be applied to this endpoint.

Hospitalization

Duration (in days) of hospitalization will be defined as the number of days subject is hospitalized for COVID-19-related reasons starting from the date of randomization. It will be calculated as the total number of days hospitalized, including readmissions for COVID-19-related reasons. It will also be calculated as the total number of days hospitalized, including any readmissions regardless of cause. See Section 6.5 for the plan for handling subjects who do not have data through Day 29 or die prior to Day 29.

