15. SUMMARY OF CHANGES IN THE CONDUCT OF THE STUDY OR PLANNED ANALYSES

15.1. Changes from Planned analyses for BET-B

The BET-B protocol and SAP inadvertently did not include analysis of Day 8 ordinal score endpoint. As this endpoint is the primary endpoint for BET-A and BET-C, the BET-B planned analyses are updated as described in this section to include Day 8 ordinal score as a secondary endpoint for BET-B. The Day 8 ordinal score analysis will only be based on complete data only, without the use of multiple imputation. Imputations for intermittent missingness described in Section 6.5 will be used. Subjects missing Day 8 score after last assessment for subjects with a good discharge status (i.e., discharged to a location other than LTAC, hospice care, other hospital) at last assessment will be assigned a score of 2 and last observation carried forward will be used for subjects missing data at Day 8 without a good discharge status (i.e., subjects with no post baseline data or still hospitalized or those discharged to LTAC, hospice care, or other hospital) at their last assessment.

Tables similar to Table 16, Table 22 will be presented for the primary subgroup (ITT Population with Baseline Ordinal Score of 5 or 6, CRP<150 mg/L, and age<85 years) and for the full ITT population. Only complete data and subgroup rows from Table 22 will be presented. Results will also be presented graphically in a figure similar to Figure 2 using complete data.

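### Time to mechanical ventilation or death: the analysis listed first uses BET-B's target subgroup, and the population that fits BET-A (baseline score 5 or 6) appears only as a subgroup row

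*SAP*

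**What the plan says.** SAP Section 8.2.2 defines the endpoint and a Cox model adjusted for baseline ordinal score, CRP, age and dexamethasone use. It then applies the model in the mITT population to "those subjects who at baseline have an ordinal score of 5 or 6, CRP<150 mg/L, and age<85 years", reported in Table 42. The next sentence adds: "This analysis will be repeated for all subjects in the mITT population and results will be reported in Table 43".

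Section 15.1, which concerns BET-B, describes that stage's "primary subgroup (ITT Population with Baseline Ordinal Score of 5 or 6, CRP<150 mg/L, and age<85 years". The three baseline limits are identical; only the base population differs (ITT there, mITT in Table 42).

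BET-A enrols more broadly. Protocol Section 5.1 asks for "Male or non-pregnant female adult ≥ 18 years of age at time of enrollment" and for "supplemental oxygen (any flow), mechanical ventilation or ECMO (ordinal score 5, 6, or 7". Neither Section 5.1 nor 5.2 contains a CRP criterion or an upper age limit.

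The key secondary endpoint built on the same events, survival without respiratory failure through Day 29, "will be analyzed only for subjects with an actual baseline ordinal score of 5 or 6" (SAP Section 6.4.2). In Table 6, CRP<150 is only one of its subgroups.

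On the reach of the Master SAP, the Preface says: "Default elements are described in this Master Statistical Analysis Plan (SAP) and align closely with BET-A study". It also says of stage-specific elements that "these supersede the corresponding elements described in this Master SAP".

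**The concern.** The limits that define Table 42 belong to another stage with another drug. Nothing in the BET-A protocol or the SAP explains why a risankizumab result should be presented first in subjects below a CRP cut-off and below 85 years. The protocol's rationale is that the drug dampens marked inflammation, so a lead table without the subjects of highest CRP needs a stated reason.

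The SAP also does not say which result leads. A programmer or reader faces a restricted Table 42 listed first, an unrestricted Table 43 called a repeat, a Table 6 entry labelled Primary without restriction, and a Kaplan-Meier figure for the whole mITT population. If the hazard ratios differ, the choice between them could be made after the data are seen.

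The reader who wants to set the time-to-event result beside the key secondary result must go to a subgroup row to find the matching population.

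**Working it through.** **Step 1. Populations side by side.**

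| Place | Baseline score | CRP<150 and age<85? | Role |
|---|---|---|---|
| SAP 8.2.2, Table 42 | 5 or 6 | yes | listed first |
| SAP 8.2.2, Table 43 overall | any, including 7 | no | repeat |
| Table 43 shell, score 5 or 6 row | 5 or 6 | no | subgroup row |
| SAP Table 6, efficacy row 12 | not limited | no | Primary; no subgroups listed |
| SAP Table 7, efficacy row 12 | not limited | no | Primary |
| Figure 11 | mITT; panels for 5, 6 and 7 singly and by dexamethasone use | no | only Kaplan-Meier plot |
| Key secondary endpoint, SAP 6.4.2 and 8.2.1 | 5 or 6 | no | key secondary |
| BET-A eligibility, Protocol 5.1 and 5.2 | 5, 6 or 7 | no | enrolment |
| BET-B, SAP 15.1 | 5 or 6 | yes | BET-B primary subgroup |

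The row for score 5 or 6 in Table 43 follows from the shell: Table 43 takes the Table 42 format, which has that row, and the implementation note adds rows for 7 and for 6 or 7. Figure 11 has no combined panel for 5 or 6. The Table 42 shell also calls for the remaining Table 6 subgroups, but Table 6 lists none for this endpoint.

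**Step 2. Why Table 43 overall is not a clean substitute.** The Table 42 shell, which Table 43 follows, counts progression to score 7 or 8. A subject with baseline score 7 is already in that state, and Section 8.2.2 does not say how the event is then timed. Leaving score 7 out is therefore reasonable; the CRP and age limits are what lack support.

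**Step 3. A stated figure to reproduce.** There is none for this endpoint. The only power figures are in Table 5, for the Day 8 ordinal score. Shifting the Table 4 distribution by an odds ratio of 2 and simulating 200,000 trials with the interim rules gives 0.760 (alpha 0.05) and 0.909 (alpha 0.20), against 0.765 and 0.913 stated. Those figures hold, and the restriction does not touch them.

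**Step 4. Precision of Table 42 against all score 5 or 6 subjects.** With 1:1 allocation, the standard error of the log hazard ratio is about 2/√D for D events. If a share f of the events lies outside Table 42, the standard error is multiplied by 1/√(1−f). The detectable hazard ratio at 80% power is exp(−(z + 0.842)·2/√D), with z = 1.960 for two-sided 0.05 and 1.282 for two-sided 0.20. The total of 40 events is an assumption.

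| f | Events in Table 42 | SE increase | Detectable HR, 0.05 | Detectable HR, 0.20 |
|---|---|---|---|---|
| 0 | 40 | none | 0.41 | 0.51 |
| 0.20 | 32 | 12% | 0.37 | 0.47 |
| 0.30 | 28 | 20% | 0.35 | 0.45 |
| 0.40 | 24 | 29% | 0.32 | 0.42 |
| 0.50 | 20 | 41% | 0.29 | 0.39 |

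**Step 5. What f might be.** The documents give no CRP or age distribution, event rate or hazard ratio for this endpoint, so only scenarios are possible. Take 200 subjects (Protocol Section 5). Assume 80–90% have score 5 or 6, 60–90% of those are kept by the limits, event risk is 15–25% in those kept and equal or double in those left out, and the hazard ratio is 0.5.

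One case: 160 subjects with score 5 or 6, 75% kept, risks 20% and 40%.

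- Events kept: 160 × 0.75 × 0.20 = 24. Events outside: 160 × 0.25 × 0.40 = 16. So f = 16/40 = 0.40.
- Power at two-sided 0.20: Φ(√24 × 0.693/2 − 1.282) = 0.66 restricted, and Φ(√40 × 0.693/2 − 1.282) = 0.82 for all 40 events.

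Over the whole grid, f runs from 10% to 57%, and power at 0.20 is about 3 to 26 points lower in Table 42 than in all score 5 or 6 subjects.

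**The case against.** The strongest reply is the sentence that follows the restriction: the analysis is repeated in all mITT subjects. It answers three stronger readings that a reader might infer.

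- **That eligible subjects are left out of the plan.** They are absent from Table 42 only. Table 43 and Figure 11 include them.
- **That no planned analysis covers all score 5 or 6 subjects.** The Table 43 shell has that row, with the adjusted hazard ratio, both confidence intervals and a p-value.
- **That the time-to-event and key secondary results cannot be read together.** That same row uses the key secondary population.

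The SAP also never calls Table 42 the main analysis. The entries labelled Primary in Tables 6 and 7 are unrestricted. The precision loss is therefore a property of Table 42 and not of the plan as a whole, and its inputs are assumed.

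The tier is low. This is an other secondary endpoint in the SAP, absent from Protocol Table 3 and from the global analysis in SAP Table 9. A common subgroup across stages may be intended for comparison, though the SAP does not say so. A BET-A SAP appendix, not among the documents, could replace the default.

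Missing baseline CRP is not part of this point. CRP is also a covariate in the unrestricted Cox model, so changing the population would not resolve it.

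All of this stands. It reduces the point to which population leads, but it does not supply a BET-A reason for the CRP and age limits or settle the disagreement between Section 8.2.2, Table 6 and Figure 11.

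**Conclusion.** The point holds in limited form. Neither headline result suits BET-A: Table 42 carries another stage's limits, and the Table 43 overall result includes subjects ventilated at baseline. The suitable population is already planned, but without lead status.

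The 12–41% increase in standard error rests on an assumed 20–50% of score 5 or 6 events lying outside Table 42. It applies only if Table 42 is read as the lead result. The primary endpoint, its power and the interim rules are unaffected. The conclusion concerns the Master SAP default as supplied. The change is worth making before unblinding, but it is not critical.

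**What to change.** For BET-A, state in SAP Section 8.2.2 or in the BET-A appendix that the lead population for time to mechanical ventilation or death is mITT subjects with actual baseline score 5 or 6, as for the key secondary endpoint. Keep the CRP<150 mg/L and age<85 set as a named subgroup for cross-stage comparison, and keep the whole-mITT run as supportive.

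Then align the rest:

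- give the lead population and the subgroup in Table 6, row 12;
- retitle Tables 42 and 43 to match;
- add a combined score 5 or 6 panel to Figure 11.

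The cost is SAP wording, table titles and one figure panel. No new data are needed, and the model is unchanged.
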